4.2 Subgroups

No subgroup analyses are planned.

5. Definitions

Age

Subject age at randomization will be determined using the age in years reported in the clinical database.

Treatment-Emergent Adverse Event:

A treatment-emergent adverse event (TEAE) is any adverse event that begins or

worsens after the initial dose of investigational product as determined by the flag indicating the adverse event started after the first dose on the Events case report form (CRF) and ends prior to or at end of the study.

Baseline:

For any variable, unless otherwise defined, baseline is the last assessment taken prior

to the first dose of investigational product.

Baseline ECG:

Baseline for ECG data is defined as the pre-dose assessments on day 1.

As per protocol, predose ECGs will be performed on 3 occasions separated by at least 30 minutes all in triplicate for a total of 9 ECGs (3 sets of triplicate ECGs) at -90, -60 and -30 minutes before investigational product administration.

Baseline will be calculated by calculating the means of each of the triplicate predose observations separately and finally establishing the mean of those 3 separate means of triplicates.

Change from Baseline:

Change from Baseline is the arithmetic difference between Post-baseline and Baseline.

Change (absolute) from Baseline = (Post-baseline Value – Baseline Value)

Change (percent) from Baseline = [(Post-baseline Value - Baseline Value) /

Baseline Value] x 100

Enrollment Date:

The enrollment date is defined as the randomization date. This is scheduled to be

Day -2 for Cohorts 1, 3 and 5, and Day -1 for Cohorts 2, 4 and 6 and day -28 for cohort 7.

Investigational Product:

The term investigational product is used in reference to AMG 598 or placebo.

Non-investigational Product:

Liraglutide is the non-investigational product used in this study.

Primary Completion:

The primary completion date is defined as the date when the last subject is assessed or receives an intervention for the final collection of data for the primary endpoint(s), for the purposes of conducting the primary analysis, whether the study concluded as planned in the protocol or was terminated early.

If the study concludes prior to the primary completion date originally planned in the protocol (ie, early termination of the study), then the primary completion will be the date when the last subject is assessed or receives an intervention for evaluation in the study (ie, last subject last visit).

End of Study:

The end of study date is defined as the date when the last subject across all sites is assessed or receives an intervention for evaluation in the study (ie, last subject last visit), following any additional parts in the study (eg, long-term follow-up), as applicable.

Screening Date:

The screening date is defined as the date the informed consent is signed.

Study Day 1:

Day 1 is defined as the first day that investigational product is administered to the subject.

Study Day:

Post study day 1: study day = (study date - date of Study Day 1) + 1

Pre study day 1 = (study date – date of Study Day 1)

Fridericia-corrected QT Interval (QTcF)

The Fridericia correction will be calculated from the investigator reported QT (msec) and RR interval (msec), as follows: QTcF=QT/(RR/1000)^{1/3}

Bazett-corrected QT Interval (QTcB)

The Bazett's correction will be calculated from the investigator reported QT (msec) and RR interval (msec), as follows: QTcB=QT/(RR/1000)^{1/2}

6. Analysis Sets

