9.2.3.1 Adverse Events

9.2.3.1.1 Time Period and Frequency for Collecting and Reporting Safety Event Information

9.2.3.1.1.1 Adverse Events

The adverse event grading scale to be used for this study will be the Clinical Adverse Event Severity Grading Scale and is described in Section 12.4.

The investigator is responsible for ensuring that all adverse events observed by the investigator or reported by the subject that occur after the first dose of AMG 598/placebo through the end of study are reported using the Event CRF.

9.2.3.1.1.2 Serious Adverse Events

The investigator is responsible for ensuring that all serious adverse events observed by the investigator or reported by the subject that occur after the informed consent through end of study are reported using the Event CRF. All serious adverse events will be collected, recorded and reported to the sponsor or designee within 24 hours, as indicated in Section 12.4. The investigator will submit any updated serious adverse event data to the sponsor within 24 hours of it being available.

9.2.3.1.1.3 Serious Adverse Events After the Protocol-required Reporting Period

There is no requirement to monitor study subjects for serious adverse events following the protocol-required reporting period or after end of study. However, these serious adverse events can be reported to Amgen. Per local requirements in some countries, investigators are required to report serious adverse events that they become aware of after end of study. If serious adverse events are reported, the investigator is to report them to Amgen within 24 hours following the investigator's knowledge of the event.

Serious adverse events reported outside of the protocol-required reporting period will be captured within the safety database as clinical trial cases and handled accordingly based on relationship to investigational product.

The method of recording, evaluating, and assessing causality of adverse events and serious adverse events and the procedures for completing and transmitting serious adverse event reports are provided in Section 12.4.

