7.2 Primary Analysis

The primary analysis will occur after all subjects from cohorts 1 to 6 have completed the study and it will include all subjects from cohorts 1 to 6.

Data from cohort 1 to 6 will be locked prior to primary analysis is carried out and clean snapshot data from cohort 1 to 6 will be used for primary analysis.

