8.3 Handling of Missing and Incomplete Data

The frequency of missing and incomplete data is expected to be low in this study and therefore, missing data will not be imputed.

Laboratory measurements that are below the quantification limits will be considered equal to the lower limit of quantification (LLQ) for the calculation of population averages as a part of the summary tables. There will be no imputation of clinical laboratory values below LLQ for individual subject level data in line listings.

Biomarker data that are below the quantification limits will be considered equal to half of the LLQ for all analyses unless specified otherwise.

PK concentrations that are below the quantification limits will be set to zero when engaging non-compartmental model to compute PK parameters.

For partial dates (such as treatment emergent AE, concomitant medication, drug administration etc.), imputation of dates will be carried out as per Appendix A.

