9.7.2.3 Whole Body Composition by DXA

Summary of absolute and percent change from baseline values in body composition, including measures of total bone mineral context (BMC), total fat mass, total lean mass and visceral adipose tissue (VAT), as measured by whole body DXA will be summarized for subjects in cohort 7.

9.7.2.4 Weight, Waist Circumference and BMI:

Summary of absolute and percent change from baseline values in body weight, weight circumference and BMI will be summarized.

Mean percent change from baseline in weight by visit for all treatment groups will also be graphed.

10. Changes From Protocol-specified Analyses

There are no changes to the protocol-specified analyses.

11. Literature Citations / References

Amgen. AMG 598 Investigator's Brochure, Edition 1.

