Appendix A. Handling of Missing or Incomplete Dates for Adverse Events and Concomitant Medications

14.1.1 Imputation Rules for Partial or Missing Stop Dates:

If the month and year are present, impute to the last day of the month.

If only the year is present, impute December 31 of that year.

If the stop date is entirely missing, assume the event or medication is ongoing. If a partial or complete stop date is present and the 'ongoing' or 'continuing' box is checked, then it will be assumed that the AE or conmed stopped and the stop date will be imputed, if partial.

	Stop Date							
		Complete: yyyymmdd		Partial: yyyymm		Partial: yyyy		
Start Date		<1 st Dose	≥1 st Dose	<1 st Dose yyyymm	≥1 st Dose yyyymm	<1 st Dose yyyy	≥1 st Dose уууу	Missing
Partial: yyyymm	Equal to 1 st Dose yyyymm		1		1	N/A	1	1
	Not equal to 1 st Dose yyyymm	2	2	2	2	2	2	2
Partial:	Equal to 1 st Dose yyyymm		1		1	N/A	1	1
уууу Уууу	Not equal to 1 st Dose yyyymm	3	3	3	3	3	3	3
Mis	sing	4	1	4	1	4	1	1

14.1.2 Imputation Rules for Partial or Missing Start Dates:

1 = Impute the date of first dose

2 = Impute the first of the month

3 = Impute January 1 of the year

4 = Impute January 1 of the stop year

Note: For subjects who were never treated (first dose date is missing), partial start dates will be set to the first day of the partial month.

Note: If the start date imputation leads to a start date that is after the stop date, then do not impute the start date.

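### The SAP's TEAE definition requires the event to have ended, so read literally it drops unresolved adverse events from a primary endpoint

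*SAP*

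**What the plan says.** SAP section 5 (Definitions) sets two conditions for a TEAE. The event must begin or worsen after the initial dose, and the flag that establishes this is described as showing that it "started after the first dose on the Events case report form (CRF) and ends prior to or at end of the study". The same section makes end of study a trial-level date: "The end of study date is defined as the date when the last subject across all sites is assessed" or receives an intervention, that is, last subject last visit.

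SAP Appendix A deals with missing dates: "If the stop date is entirely missing, assume the event or medication is ongoing". If the start date is missing as well, its table points to code 1: "1 = Impute the date of first dose". SAP section 8.3 names TEAE dates among the partial dates for which "imputation of dates will be carried out as per Appendix A".

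SAP section 7.2 says that cohorts 1–6 are locked first and that "clean snapshot data from cohort 1 to 6 will be used for primary analysis". SAP section 10 states: "There are no changes to the protocol-specified analyses".

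Protocol section 9.2.3.1.1.1 requires reporting of all adverse events "that occur after the first dose of AMG 598/placebo through the end of study are reported using the Event CRF", with no resolution requirement. The Protocol Synopsis, under the end-of-study visit, lets follow-up of treatment-emergent events finish at resolution, at stability in the investigator's opinion, or at loss to follow-up. Protocol section 9.2.3.1.3 is similar for all adverse events, and Appendix 4 (section 12.4) asks for a resolution date only where the event has resolved.

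**The concern.** The subject of the verb in the closing clause is the adverse event, so an event that has not ended does not qualify. A definition meant to set an onset window has become a filter on resolution.

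TEAE incidence is a primary endpoint (Protocol section 4.1). SAP section 9.6.2 uses TEAEs for overall incidence and for the tables by system organ class and preferred term, by grade, and by relationship to each product, so all of these inherit the definition. A programmer who follows the text would leave out events still open at the end, and a safety reader particularly wants to see those. Because SAP section 10 declares no changes, nothing alerts a reader to a narrower count than the protocol implies.

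**Working it through.** **1. Does an ongoing event meet the SAP definition?**

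- Onset: yes. The Events CRF flag records that the event started after first dose. It carries no information on when the event ended.
- End: no. Appendix A treats a missing stop date as ongoing and imputes no end date, so there is nothing to satisfy the clause.
- An event whose stop date falls after last subject last visit also fails.
- For cohorts 1–6, a stop date recorded after the lock is not in the snapshot, so it cannot bring the event back into the primary analysis. An event that is closed as stable may never acquire a stop date.

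**2. Is this what the protocol implies?** The protocol has no formal TEAE definition. Its collection window is set by occurrence, and its synopsis calls events treatment-emergent even when they only stabilise or the subject is lost. Both conflict with a resolution requirement.

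**3. The plan's own figure that depends on counting events.** Protocol section 10.1 and SAP section 3.2 give the chance of seeing at least one event among 66 AMG 598 subjects as 96.6% at 5% incidence and 99.9% at 10%. The formula is 1 − (1 − p)^66:

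- p = 0.05: 0.9661, which reproduces 96.6%.
- p = 0.10: 0.9990, which reproduces 99.9%.

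Under the literal clause, countable incidence is p(1 − u), where u is the share of affected subjects whose event is unresolved. The documents do not give u; the values below are assumptions.

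| u | Detection, p = 5% | Detection, p = 10% | Expected subjects counted at p = 5%, 66 × 0.05 × (1 − u) |
|---|---|---|---|
| 0 | 96.6% | 99.9% | 3.30 |
| 10% | 95.2% | 99.8% | 2.97 |
| 20% | 93.2% | 99.6% | 2.64 |
| 30% | 90.5% | 99.2% | 2.31 |
| 50% | 81.2% | 96.6% | 1.65 |

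**4. Overall TEAE incidence.** A subject is lost from the overall count only if every event he or she has is unresolved. Assume 60% true incidence, k events per affected subject, and each event independently unresolved with probability u (here a per-event probability). Reported incidence is 0.60 × (1 − u^k).

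| k | u = 10% | u = 20% | u = 30% |
|---|---|---|---|
| 1 | 54.0% | 48.0% | 42.0% |
| 2 | 59.4% | 57.6% | 54.6% |
| 3 | 59.9% | 59.5% | 58.4% |

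For example, k = 2 and u = 0.3 gives 0.60 × (1 − 0.09) = 0.546.

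**5. Preferred-term counts.** A term reported once per subject behaves as k = 1, so its count falls by the full 10%, 20% or 30%.

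**6. What one lost subject is worth.** Each active arm of cohorts 1–6 has 6 subjects. Each pooled placebo group has 2 × 3 = 6. One subject is 1/6 = 16.7 percentage points. In a cohort 7 arm of 30 it is 1/30 = 3.3 points.

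**The case against.** The strongest reply is that nobody would program it this way. The clause reads like a garbled onset window, the operative flag is an onset flag, and SAP section 9.6.2 specifies no stop-date filter. Appendix A handles ongoing events, is applied to TEAE dates, and places an event with neither date at first dose, inside the treatment period. That is good evidence of intent, and the intent was probably sound. It is not an override: one part of the SAP handles ongoing events as on-treatment while the definition excludes them.

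A second reply is that there is no protocol TEAE definition to contradict. That is true as far as it goes, and it softens the point about SAP section 10. The conflict with the collection window and with the synopsis's own use of the term remains.

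A third is that the effect is assumed and may be small. The 60%, the unresolved shares and the independence are not in the documents, and with several events per subject overall incidence hardly moves. Protocol Appendix 4 also asks for a separate record at each increased severity. If earlier-grade records carry their own end dates, which is an inference, a worsened but ongoing event might still leave a countable record. This limits the overall figure more than the counts for single-record terms.

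Finally, the analyses are descriptive, and neither dose-level reviews nor stopping rules use the SAP definition, so escalation decisions are unaffected. That stands. It bounds the consequence to the reported primary safety tables.

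**Conclusion.** The concern holds. As written, the SAP excludes unresolved adverse events from the TEAE tables, against the protocol's occurrence-based window. Confidence is high that the wording is wrong. Whether the programmed derivation actually drops events cannot be seen from the documents.

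The size is unknown. Under the assumptions above, the loss in overall incidence ranges from 0.1 points (three events per subject, 10% unresolved) to 18 points (one event, 30% unresolved), and single-report preferred terms lose the full unresolved share. Subjects who also have a resolved TEAE still count overall. No direction of bias between arms is established.

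The finding covers the TEAE tables only. The SAP does not say whether the serious-event and event-of-interest tables are limited to TEAEs, and laboratory, vital-sign, ECG and DXA summaries are not affected. Because the error sits in the definition of a primary endpoint and costs almost nothing to remove, it must be fixed.

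**What to change.** Replace the definition in SAP section 5 with wording to this effect: *a TEAE is any adverse event whose onset or worsening falls after the subject's first dose of investigational product and no later than end of study, irrespective of whether, or when, it resolves.* The Events CRF flag can stay as the onset criterion. Adverse events are collected only up to each subject's own end-of-study visit, so keeping the existing end-of-study bound does not widen the window in practice; the sentence could name that visit if the team wants to remove any doubt.

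The cost is one SAP sentence and a check that the TEAE derivation applies no stop-date condition. If the programs already ignore the clause, no result changes and the text then matches the code.

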6.1 Safety Analysis Set

The safety analysis set will consist of all subjects who receive at least one dose of investigational product.

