6.5 Final Analysis set

The final analysis set will consist of all subjects from cohort 7 who receive at least one dose of investigational product.

7. Planned Analyses

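### For cohort 7 the SAP gives the wrong randomisation day and, separately, words its analysis sets, Study Day 1 and general baseline so that the run-in placebo is not excluded

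*SAP*

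**What the plan says.** SAP section 5 states "The enrollment date is defined as the randomization date" and gives the scheduled day as "Day -2 for Cohorts 1, 3 and 5, and Day -1 for Cohorts 2, 4 and 6 and day -28 for cohort 7". The same section says "The term investigational product is used in reference to AMG 598 or placebo", with no exception for a run-in injection. Its general baseline rule is "For any variable, unless otherwise defined, baseline is the last assessment taken prior" to the first IP dose, and for Study Day 1 it says "Day 1 is defined as the first day that investigational product is administered to the subject".

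SAP 6.1 reads "The safety analysis set will consist of all subjects who receive at least one dose of investigational product". SAP 6.5 reads "The final analysis set will consist of all subjects from cohort 7 who receive at least one dose of investigational product". SAP section 10 states "There are no changes to the protocol-specified analyses".

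The protocol is more specific:

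- Sections 6 and 6.6 enrol cohort 7 on the Part 1 criteria at screening. Randomisation follows only if the subject completes the run-in and meets the Part 2 criteria. Section 7.2 puts it on day 1.
- Section 9.1.2 ties day 1 for cohort 7 to the first AMG 598/placebo dose given after randomisation.
- Section 10.2.1.1 requires the qualifying dose for the Safety set to be given on day 1.
- The Synopsis and Table 2-3 (study drug row and footnote j) give every cohort 7 subject one placebo injection on day -28.
- The Appendix 1 glossary, however, defines enrolment as randomisation and gives Study Day 1 no post-randomisation anchor.

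**The concern.** There are two separate defects.

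**(a) The date.** A cohort 7 subject cannot be randomised on day -28, because randomisation depends on finishing the run-in that starts that day. A run-in failure never has a randomisation date, so under the SAP that subject has no enrolment date either, although protocol 6.6 counts the subject as enrolled. SAP 9.2 bases disposition on enrolled subjects and lists those screened but not enrolled as screen failures. It does not say where a run-in failure belongs.

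**(b) The anchors.** For cohorts 1 to 6 the first IP dose is the day 1 dose, so the omitted words do no harm. Cohort 7 has a placebo injection four weeks earlier, and nothing in the SAP says that it is not IP. A programmer who follows the text exactly could count it as the first dose for set membership, Study Day 1, the general baseline and exposure.

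**Working it through.** **1. The protocol's own timeline.** Protocol 5.3.2 gives cohort 7 a 28-day screening period, a 28-day run-in and up to 207 days on study: 28 + 28 + 207 = 263 days, as stated. The 207-day count therefore starts after the run-in, and day 1 is the first post-randomisation dose.

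**2. SAP against protocol, cohort 7.**

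| Item | Protocol | SAP |
|---|---|---|
| Enrolment | After Part 1 criteria, before run-in (6.6); glossary: randomisation | Same as randomisation (5) |
| Randomisation | Day 1, after run-in (6, 6.6, 7.2) | Day -28 (5) |
| Day 1 | First post-randomisation dose (9.1.2); glossary: no such anchor | First day of IP (5) |
| Safety set | IP dose on day 1 (10.2.1.1) | Any IP dose (6.1) |
| Cohort 7 Final set | None defined | Any IP dose (6.5) |

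**3. Study days on the literal reading.** SAP section 5 sets study day = date - date of Study Day 1 + 1. If the day -28 injection were Study Day 1, protocol day d (d ≥ 1) would become (d - 1) + 28 + 1 = d + 28. Day 1 becomes 29 and day 207 becomes 235. The SAP's own footnote in section 3.1 keeps end of study at day 207, so this result is evidence against the literal reading.

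**4. Span of weight change to day 85 (nominal days, visit windows ignored).**

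- From day 1, as the protocol intends: 85 - 1 = 84 days.
- From a day -28 weight taken before the injection: 84 + 28 = 112 days.
- From screening (days -29 to -56), if the day -28 weight is not pre-injection: 84 + 29 = 113 to 84 + 56 = 140 days.

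Table 2-3 schedules a weight on day -28 but marks only the day 1, 29 and 57 weights as pre-dose, so the documents do not settle which span would apply.

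**5. IP doses.** Table 2-3 marks study drug on days -28, 1, 29 and 57. That is 4, against the planned 3.

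**6. Measures without a baseline.** These have change-from-baseline summaries planned in SAP 9.7.2 and no scheduled value before the day -28 injection:

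- waist circumference: 1
- insulin, C-peptide, GIP, GLP-1 and glucagon: 5
- free fatty acids: 1
- whole-body DXA (bone mineral content, fat mass, lean mass, visceral fat): 4

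The total is 1 + 5 + 1 + 4 = 11. Pharmacodynamic (PD) glucose makes it 12 unless the screening glucose may serve as its baseline. Protocol Table 12-1 lists chemistry glucose (local laboratory) and PD glucose (central laboratory) separately, so either count can be argued.

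**7. Set membership.** A subject who receives the day -28 placebo and fails the run-in is removed unrandomised (protocol 6.6). That subject fails the protocol's Safety set definition but meets SAP 6.1 and 6.5 as worded. The documents give no run-in failure rate, so the number of such subjects cannot be derived.

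**The case against.** The strongest reply is that nobody would program the literal reading. The SAP's labels of day -56, day -28 and day 207 work only if day 1 is the first randomised dose. SAP section 1 says that the plan details the analyses of protocol amendment 3, and section 10 declares no changes, which suggests that the protocol's definitions still govern. The protocol also treats run-in failures as not yet having received AMG 598/placebo (6.6) and names the run-in placebo separately (9.1.1). Adverse events are collected only after the first AMG 598/placebo dose (9.2.3.1.1.1). In the SAP, treatment-emergent status follows a CRF flag, ECG baseline is fixed to day 1, and by-visit tables use protocol time points (9.1). All of this stands as evidence of intent, and it is why the point is minor. It does not make the set, baseline and IP definitions correct as written.

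Three narrower replies also stand. Day -28 is a reasonable enrolment date and is wrong only as a randomisation date. The protocol has no Final analysis set, so nothing was dropped from one; the SAP's own set simply lacks an anchor. The protocol is also inconsistent, because its glossary conflicts with sections 6.6 and 9.1.2.

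A reader might infer that the wrong randomisation date causes the problems with sets and baseline. It does not: none of those definitions uses the enrolment or randomisation date. They arise only from the missing anchors combined with the unqualified IP definition.

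**Conclusion.** The point holds as two separate wording defects, of minor severity. The date conflict in (a) needs no interpretation. Defect (b) is an ambiguity. Its literal consequences are never-randomised subjects in the Safety and Final sets, a 112-day weight span (113 to 140 from screening) instead of 84, 4 IP doses instead of 3, and 11 or 12 measures without a baseline. The 112 assumes that the day -28 weight precedes the injection; the 11 assumes that screening glucose can serve as the PD glucose baseline.

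Two stronger inferences are not supported. One is that the SAP plans a different analysis population: its day labels and section 10 point the other way. The other is that the cohort 7 weight comparison would be biased towards one arm: both randomised arms share the same run-in, so an earlier baseline would add run-in drift to each. Any effect on placebo adverse event incidence cannot be sized from the documents.

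**What to change.** In the SAP:

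1. Require an IP dose on day 1, after randomisation, for the Safety set (6.1) and the cohort 7 Final set (6.5).
2. State in section 5 that the day -28 run-in placebo is not IP for analysis. Anchor cohort 7 Study Day 1, the general baseline and IP dose counts to the first post-randomisation dose.
3. Define the cohort 7 enrolment date (per protocol 6.6) and randomisation date (day 1) separately, and say how SAP 9.2 reports run-in failures.

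Reconcile the protocol glossary entries for Enrollment and Study Day 1 with sections 6.6 and 9.1.2, at the next amendment or in a note to file. The cost is wording only. No new data are needed, and the anchors in item 1 (for the Safety set) and item 2 already stand in the protocol.
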